APPENDIX I:

DEFINITIONS OF NEONATAL MORBIDITY/MORTALITY

Neonatal Death and Stillbirth: Intrauterine fetal demise at a viable gestational age or neonatal death within 28 days of delivery

Intraventricular Hemorrhage (IVH): determined by cranial ultrasound or computed tomography

Grade I	subependymal hemorrhage
Grade II	intraventricular hemorrhage, uncomplicated
Grade III	intraventricular hemorrhage with ventricular dilatation
Grade IV	intraventricular hemorrhage with ventricular dilatation and parenchymal extension

Periventricular Leukomalacia (PVL): all PVL is determined by cranial ultrasound

- Any PVL
- Cystic PVL

Necrotizing Enterocolitis (NEC)

Stage I: Other – Suspect

• Treatment was observation

Stage II: Clinical – Definite

• Treatment was medical

Stage III: Surgical – Advanced

• Treatment was surgical

Respiratory Distress Syndrome (RDS): requires both diagnosis and oxygen therapy

- For the purpose of the study diagnosis must include:
 - oxygen therapy ($\text{FiO}_2 \geq 0.40$) until infant death or ≥ 24 hours **and**
 - a clinical diagnosis of RDS

Retinopathy of Prematurity (ROP)

- Stage I Ophthalmoscopic demarcation line of normal and abnormal vessels
- Stage II Intra-retinal ridge (ridge that rises from the retina as a result of the growth of the abnormal vessels)
- Stage III Ridge with extraretinal fibrovascular proliferation (the ridge grows from the spread of the abnormal vessels and extends into the vitreous)
- Stage III+ Stage III and “plus disease” meaning that the blood vessels of the retina have become enlarged and twisted, indicating a worsening of the disease.
- Stage IV Partially detached retina.
- Stage V Complete retinal detachment.

Bronchopulmonary Dysplasia (BPD)

- Treatment with $> 21\%$ oxygen for at least 28 days, **or**
- Oxygen dependence after 36 weeks post-conceptional age

Sepsis: Must include

- Blood culture proven sepsis, **and**
- a Clinically ill infant with infection defined as:
 - Bacterial sepsis of the newborn
 - Streptococcal sepsis
 - Severe sepsis

Neonatal Seizure

- Any incident(s) documented as evidence of seizure/epileptic activity by the neonatal staff,

DEFINITIONS OF COMPOSITE PERINATAL MORTALITY/NEONATAL MORBIDITY OUTCOME SCORES:

0 to 4 scale with NICU* (NMI): This score is defined as the following:

0 = no events,
1 = one event for (RDS, BPD, grade III or IV IVH, any PVL, proven sepsis, or NEC) or <1-4 days in the NICU, and no perinatal mortality;
2 = two events or between 5 and 20 days in the NICU, and no perinatal mortality;
3 = three or more events or >20 days in the NICU, and no perinatal mortality;
4 = perinatal mortality.

Morbidities with high likelihood of major chronic illness (MNM): This score is defined as the following:

0 = no events,
1 = one or more events for (cystic PVL, BPD, grade III or IV IVH, stage III or higher ROP, NEC requiring surgical treatment)

*Adapted from Hassan SS, et al. Ultrasound Obstet Gynecol 2011; 38:18-31
Supplementary Information

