5.1 Analysis Populations

One control population will be considered in primary analyses: the historical control population. The historical control population includes all subjects who attended ChristianaCare during the eligibility period and who satisfy all eligibility criteria.

The historical control arm will be the control population for primary and alternative analysis of the primary, secondary and exploratory endpoints.

Seven subject populations will be considered in the analyses: an Intent-to-Treat (ITT) population, a modified ITT population, a completer(s) population, a compliant completers population, a non-intervention completers population and a safety population. The completers, compliant completers, non-intervention completers and modified ITT populations are subsets of the ITT population.

The ITT population includes all historical subjects selected and all prospective patients enrolled regardless of whether or not the co-primary outcomes were observed, or in the prospective arm, any PreTRM test result has been generated or intervention consent has been signed. Subjects with missing outcomes will be handled as described in the missing data sensitivity analyses.

The modified ITT (mITT) population includes all subjects for whom both co-primary outcomes are known; and who have either been selected for the historical control group, received a not-higher-risk PreTRM® test result, or consented to and initiated treatment before 24^{0/7} weeks gestation after receiving a higher risk PreTRM® test result.

The completers population includes subjects for whom both of the co-primary outcomes are known, and, in the prospective arm, for whom a PreTRM® test result was generated.

The compliant completers population includes ITT subjects who have missed no more than 20% of daily doses for both low-dose aspirin and vaginal progesterone, and participated in weekly care management calls with no more than 20% missed weeks.

The non-intervention completers population includes all ITT subjects who received a higher-risk PreTRM® test result but neither consented to nor initiated treatment before 24^{0/7} weeks gestation.

The safety population includes all eligible subjects who gave consent to participate in the study and attempted a blood draw for the PreTRM® test, regardless of receipt of study interventions.

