5.7 Exploratory Analyses

In AVERT, there is a challenge and opportunity in the moderate rate of acceptance of intervention among high-scoring women in the intervention arm. The exploratory analyses include options for addressing the non-accepting completers in the prospective arm, and comparing them to those in mITT and the compliant completers.

The exploratory outcomes will be summarized within the prospective arm and within historical controls using descriptive statistics and graphical displays where appropriate. Continuous outcomes will be summarized using sample size (n), means, medians, standard deviations, and ranges. Categorical outcomes will be summarized using frequency and percentages. Estimates will be presented with 95% confidence intervals. Exploratory summaries will be performed for the mITT population.

The following exploratory endpoints will be evaluated by a test of proportions in the prospective arm versus historical controls. The null hypothesis is no difference between historical controls and the prospective arm. The alternative hypothesis is relative reduction in proportion of occurrence of one or more conditions in the prospective arm as compared to historical controls. Statistical testing for these endpoints will be performed using a logistic regression model with covariates as specified above for the primary analysis, and with propensity scoring adjustment as specified for the alternative analysis.

- Reduction in occurrence of one or more major neonatal morbidities with high likelihood of major chronic illness (MNM): cystic periventricular leukomalacia,

- grade 3 and 4 intraventricular hemorrhage, grade 3 or higher retinopathy of prematurity, bronchopulmonary dysplasia.
- Reduction in the rate of PTB <35 weeks, <32 weeks and <37 weeks of gestation. This analysis will be repeated for premature neonates delivered after spontaneous rupture of membranes or spontaneous onset of labor with gestational age at birth <32, <35 and <37 weeks vs. all other neonates.
- Reduction in NICU admission rates in the immediate neonatal period prior to initial discharge or neonatal death. This analysis will be repeated for all premature neonates, and for premature neonates delivered after spontaneous rupture of membranes or spontaneous onset of labor.

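### The exploratory endpoint MNM has no level for death, so deaths that replace would-be MNM cases lower the tested rate in whichever arm they occur

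*SAP*

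**What the plan says.** Appendix I of the SAP introduces the score with "Morbidities with high likelihood of major chronic illness (MNM): This score is defined as the following" and sets it to 0 for no events and otherwise "1 = one or more events for (cystic PVL, BPD, grade III or IV IVH, stage III or higher ROP, NEC requiring surgical treatment". Section 5.7 lists the endpoint as "Reduction in occurrence of one or more major neonatal morbidities with high likelihood of major chronic illness (MNM" and names its components without death. Neither place counts a death as an event, excludes it, or treats it as a competing event.

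The endpoint is tested, not only described: "Statistical testing for these endpoints will be performed using a logistic regression model with covariates". The test has a direction: "The alternative hypothesis is relative reduction in proportion of occurrence of one or more conditions in the prospective arm as compared to historical controls".

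Section 5.4 applies the primary and alternative analyses to the exploratory endpoints in the mITT population. Section 5.1 defines that population: "The modified ITT (mITT) population includes all subjects for whom both co-primary outcomes are known". It adds conditions on the test result and treatment in the prospective arm. No condition concerns the infant's survival.

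For BPD, Appendix I requires "Treatment with $> 21\%$ oxygen for at least 28 days" or, alternatively, oxygen dependence beyond 36 weeks post-conceptional age.

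**The concern.** Death competes with MNM. An infant who has died can no longer acquire a listed diagnosis, and with only two levels the score leaves that infant among those without events. A lower MNM proportion is read as benefit, whether it comes from healthier survivors or from infants who died instead of surviving with BPD or severe IVH. The reverse also holds: a strategy that keeps very preterm infants alive can raise the MNM proportion and look harmful. The infants affected are those at the lower end of gestational age, where section 5.7 itself places most of the consequences of preterm birth.

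The plan handles death differently elsewhere. The same stillborn infant gets the worst value on both co-primary endpoints and the best value on MNM.

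**Working it through.** **1. Scoring rule followed through.**
- A stillborn infant has none of the listed diagnoses, so MNM = 0.
- An infant born at 24 weeks who dies on day 10 reaches 24 weeks + 10 days = 25 weeks 3 days. That is short of 28 days of oxygen and of 36 weeks post-conceptional age, so BPD cannot be met. Unless severe IVH, cystic PVL, surgical NEC or advanced ROP was recorded first, MNM = 0.
- An infant with one of those diagnoses before death still scores 1.

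**2. Do deaths stay in the denominator?** mITT requires both co-primary outcomes to be known. Under section 3.7 both are defined for a perinatal death: NMI is 4, and NNOLOS is set one day beyond the longest stay recorded. The SAP does not say outright that these infants remain in the MNM analysis, but nothing removes them.

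**3. Treatment of death elsewhere in the SAP.**

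| Outcome | Section | Value given to death |
|---|---|---|
| NMI | 3.7, Appendix I | 4, the worst level |
| NNOLOS | 3.7 | longest stay + 1 day |
| NICULOS | 3.7 | longest stay + 1 day (stillbirth or death in the NICU) |
| Exploratory stay endpoints | 5.7 | longest stay + 1 (perinatal deaths for hospital stay, NICU deaths for NICU stay) |
| MNM | 5.7, Appendix I | none; 0 by the literal rule |

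The RDS definition in Appendix I also provides for early death in its oxygen criterion. The BPD definition does not.

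**4. Illustration of size.** The SAP states no rate, sample size or power for MNM, so there is no figure to reproduce. All rates below are assumed.

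Inputs: 1,453 prospective and 10,000 historical (section 4). The risk of death or MNM, *c*, is equal in the two arms. Every extra screened-arm death replaces an MNM case. Then MNM rate = *c* − death rate, and ratio = screened MNM / control MNM. The last column is the chance that a one-sided 0.05 test of two proportions declares a reduction; the one-sided level is also an assumption, taken from the directional alternative.

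| *c* | Control death | Control MNM | Screened death | Screened MNM | Ratio | P(reject) |
|---|---|---|---|---|---|---|
| 2.0% | 0.5% | 1.5% | 0.8% | 1.2% | 0.80 | 0.206 |
| 2.0% | 0.5% | 1.5% | 1.0% | 1.0% | 0.67 | 0.432 |
| 2.5% | 0.5% | 2.0% | 1.0% | 1.5% | 0.75 | 0.348 |
| 1.3% | 0.3% | 1.0% | 0.6% | 0.7% | 0.70 | 0.265 |

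In every row the ratio for death or MNM is 1.00. The mITT prospective arm will be smaller than 1,453, which would lower the last column somewhat.

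The reverse case: with *c* = 2.0% and control deaths 0.5%, screened-arm deaths of 0.2% give MNM of 2.0 − 0.2 = 1.8%, a ratio of 1.8 / 1.5 = 1.20. Better survival appears as harm.

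**5. Deaths that do not displace MNM.** If the infant would have scored 0 alive, the score is 0 either way. Numerator and denominator are unchanged.

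**The case against.** The strongest reply is that MNM is meant to be narrow. Its name concerns chronic illness in survivors, and adding death changes the question. MNM is exploratory, outside the Holm family of 5.5 and outside the secondary endpoints of 5.6, and the endpoints that carry the conclusion already penalise death. Section 5.7 also plans to describe the individual components of the morbidity/mortality index, so an excess of deaths should be visible there and at NMI level 4. All of this stands and limits how much the point matters. It does not correct the MNM test, which keeps deaths in the denominator as event-free. An endpoint meant for survivors would have to say so. MNM also sits in Appendix I under a heading for scores that combine perinatal mortality with neonatal morbidity.

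Some stronger readings are tempting but not supported:
- *Any additional death flatters the screened arm.* Only deaths that displace MNM cases lower the rate, and this works in either arm.
- *All deaths are mis-scored.* Some had a listed diagnosis and score 1; others would have scored 0 alive.
- *A small shift would yield a false positive.* Assuming 9 MNM cases in 1,231 against 100 in 10,000, the one-sided Fisher p is 0.23. The rejection probabilities above need screened-arm deaths 1.6 to 2 times those of controls, and nothing in the SAP suggests that.
- *Stillbirths count as not admitted in the NICU-admission endpoint.* The SAP does not say this. That endpoint is worded "Reduction in NICU admission rates in the immediate neonatal period prior to initial discharge or neonatal death", which reads most naturally as live-born infants, and section 3.7 reserves a NICU stay of zero for infants admitted to the hospital. What remains is an unstated denominator.

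**Conclusion.** The point holds for MNM as an exploratory endpoint. By its literal definition, a stillborn infant, or one who dies before a listed diagnosis is possible, is scored as event-free in a directional test. This is inconsistent with how NMI, NNOLOS, NICULOS and the exploratory stay endpoints treat death. The bias can run in either direction and arises only through deaths that replace MNM cases. Its size cannot be derived from the SAP. Under the assumed rates above, the MNM ratio falls to 0.67–0.80 when the risk of death or MNM is the same in both arms. The co-primary and secondary conclusions do not depend on it. For NICU admission the SAP leaves open how stillbirths and delivery-room deaths are counted, which is a minor clarification.

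**What to change.** In section 5.7 and Appendix I, make the tested binary endpoint *perinatal death or MNM*. Use the Appendix I definition of death that already applies to NMI, and the same rule in both arms. Show MNM and death as separate descriptive rows beside it, so that the reader can see which component moves. In the same edit, align the two component lists: NEC requiring surgery is in Appendix I but not in 5.7.

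For NICU admission, state that the denominator is live births and report deaths beside it.

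The cost is wording only. Deaths are already needed to score NMI, so no new data are required. The one downside is that the tested composite no longer measures chronic morbidity alone; the separate MNM row keeps that information.
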